8.4.3 Withdrawal and Replacement of Subjects

8.4.3.1 Criteria for Subject Withdrawal

In accordance with the Declaration of Helsinki (Appendix 1) and other applicable regulations, a subject has the right to withdraw from the study at any time for any reason without prejudice to his or her future medical care by the physician or at the institution.

Subjects may withdraw from the study/schedule of assessments for any of the following reasons:

- Adverse Event. The patch treatment will be temporary discontinued for any subject with Grade 4 local skin reactions possibly, probably, or definitely related to the investigational product.
- A subject will be discontinued from further participation in the study for >2 grade 4 local skin reaction possibly, probably or definitely related to investigational product

- The Investigator decides that it is the subject's best interest to be withdrawn from the study.
- The subject is unwilling to continue in the study (consent withdrawal).
- Lack of compliance with protocol requirements and procedures.
- The Sponsor- Investigator or Regulatory Authorities, for any reason, stops the study.
- The subject fails to return to the clinic for scheduled visits and does not respond to telephone or written attempts at contact (lost to follow-up).
- Subject's death

The reason for withdrawal will be recorded in the clinical records and the electronic Case Report Form (eCRF) and reported annually in the IND Annual Report (21 CFR 312.33). All subjects who are withdrawn or discontinue should be provided with alternative medical care, if applicable.

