8.5.6 Dose Adjustments and Dose Escalation

No dose adjustments or dose escalation are planned apart from the adjustment in the duration of application during the first weeks of treatment.

Even though the subjects should ideally reach the daily 24-hour application regimen from the 15th day of patch application onwards, for subjects who may experience some severe local reactions at the initiation of the treatment, the daily duration of patch application should be adapted/reduced if necessary, to limit the severe reactions.

In case of local unbearable skin reactions or in case of systemic allergic reactions, the Viaskin® patch should be removed immediately in order to allow the reactions to subside rapidly. The next patch would be re-applied only the following day at the expected time and the reactions will be observed. If or when the local severe reactions recur, the patch can be removed at that time. This process can be repeated the following days until the time the subject can bear the patch for 24 hours a day.

If a subject is having systemic symptoms including worsening of EoE symptoms, the subject will have return for study visit and possible decrease in daily exposure to the Viaskin patch with gradually increase in exposure as tolerated.

Only one dose is being investigated in this pilot study, at the highest dose of Viaskin Milk currently under development (500 µg of cow's milk proteins) due to the limited number of subjects to be recruited.

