13.6.6.1 Adverse Events

All AEs will be coded by system organ class and preferred term using MedDRA. Treatment-emergent AEs (TEAEs) will be defined as any AEs, regardless of relationship to study drug, which occur during AE collection period of study drug or any event already present that worsens in either intensity or relationship to study drug following exposure to the Viaskin®. If relationship information is missing, the TEAE will be considered drug-related.

An overall summary of TEAEs will be provided showing the number and percentage of subjects in each treatment group with any TEAE, any potentially drug-related TEAE, any severe TEAE, any serious TEAE, any TEAE leading to discontinuation, and any TEAE leading to death. The number of events will also be presented.

The number of AEs as well as the number and percentage of subjects who experienced at least one AE will be summarized by system organ class, preferred term and treatment group. The incidence of the following events will be summarized:

- Local skin tolerance: incidence, severity and duration of local TEAE at site of Viaskin® application as reported by subjects in the diary card
- TEAEs: incidence, severity and duration.
- Potentially drug-related TEAEs
- Discontinuations due to TEAEs
- Laboratory data, physical examinations, and vital signs Systemic allergic symptoms in the active and placebo groups
- Potentially drug-related systemic allergic symptoms
- SAEs
- Potentially drug-related SAEs

In addition, TEAEs will be summarized by relationship to study drug and by severity. If a subject has more than one occurrence of the same TEAE with different severities or relationship to study drug, then the TEAE will be assigned to the highest severity category and/or most related relationship category. If the intensity or relationship is missing, then the 'worst case' will be assumed (i.e., severe for intensity and drug-related for relationship).

The proportion of subjects that experience systemic allergic symptoms will be summarized by treatment. All TEAEs will be listed.

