#### **2.2.6 Safety endpoints**

The safety endpoints are:

- a. Local skin tolerance: incidence, severity and duration of local Treatment-Emergent Adverse Event (TEAE) at site of Viaskin® application as reported by subjects in the diary card.

- b.** Potentially drug-related TEAEs.
- c.** Discontinuation due to TEAEs.
- d.** Laboratory data, physical examinations, and vital signs.
- e.** Systemic allergic symptoms and relatedness to Viaskin®.
- f.** Potentially drug-related systemic allergic symptoms.
- g.** SAEs.

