#### **4.5.1 Adverse events**

All AEs will be listed/described and reported by treatment groups, subject, start date, severity, grade, causality, action taken, stop date, outcome, and absence of serious AE (*Table 16A and Table 16B*). All AEs will be coded by system organ class and preferred term using the Medical Dictionary for Regulatory Activities (MedDRA). The number of subjects who experienced at least one AE as well as the number of AEs will be summarized by system organ class and treatment group (*Table 17A and Table 17B*). The Summary of AEs (total number of subjects with AEs, total number of AEs, number of AEs per subject, severity of AEs, any serious AEs, AEs leading to discontinuation and death, ongoing AEs, and outcome) by treatment group will be presented (*Table 18*). TEAEs will be defined as any AEs, regardless of relationship to study drug, which occur during the AE collection period of study drug or any event already present that worsens in either intensity or relationship to study drug following exposure to the Viaskin® Milk. TEAE will be considered drug-related if relationship information is missing. An overall summary of TEAEs (the number and percentage of subjects with any TEAE, total number of subjects with potentially drug-related TEAE, total number of TEAEs, total number of local TEAE, number of TEAEs per subject, severity of TEAEs, any serious TEAE, any TEAE leading to discontinuation and death) by treatment groups will be provided (*Table 19A and Table 19B*). The number of subjects with adverse events on local skin reactions will be summarized (Table 20)

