**Table 15 specifications**

Repeat with ITT population and PP population separately as Table 15A and Table 15B, respectively.

Table 16A. Detailed Listing for All Adverse Events by MedDRA System Organ Class

Adverse events were classified into SOC and PT using Version XX.0 of MedDRA.

The following coding will be used:

Severity: 1=Mild, 2=Moderate, 3=Severe, 4=Life-threatening, and 5=Death.

Grade: 1, 2, 3, and 4.

Causality: 1=Unlikely related, 2=Possibly related, and 3=Probably related.

Action taken: 0=None, 1=Prescribed medication, 2=Non-medication treatment, 3=Hospitalization or prolongation, 4=Discontinued treatment.

Outcome: 1=Ongoing (no change), 2= Recovering/resolving (improving), 3=Worsened, 4=Recovered/resolved with no sequelae, 5=Recovered/resolved with sequelae (chronic stable) 6=Death.

Table 16B. Detailed Listing for All Adverse Events by MedDRA Preferred Term

Adverse events were classified into SOC and PT using Version XX.0 of MedDRA.

The following coding will be used:

Severity: 1=Mild, 2=Moderate, 3=Severe, 4=Life-threatening, and 5=Death.

Grade: 1, 2, 3, and 4.

Causality: 1=Unlikely related, 2=Possibly related, and 3=Probably related.

Action taken: 0=None, 1=Prescribed medication, 2=Non-medication treatment, 3=Hospitalization or prolongation, 4=Discontinued treatment.

Outcome: 1=Ongoing (no change), 2= Recovering/resolving (improving), 3=Worsened, 4=Recovered/resolved with no sequelae, 5=Recovered/resolved with sequelae (chronic stable) 6=Death.

Table 17A. Adverse Events by System Organ Class (Number of subjects)

Adverse events were classified into SOC and PT using Version XX.0 of MedDRA.

Table 17B. Adverse Events by System Organ Class (Number of adverse events)

Adverse events were classified into SOC and PT using Version XX.0 of MedDRA.

Table 18. Summary of Adverse Events by Treatment Group

	All	Viaskin® milk	Placebo
Number of subjects (%) with AEs			
Number of AEs			
Number of AEs per subject			
0			
1			
2 +			
Number of systemic allergic symptoms			
Potentially drug-related			
Yes			
No			
Severity of AEs			
Mild			
Moderate			
Severe			
Life-threatening			
Death			
Serious AEs (SAEs)			
Yes			
No			
Number of potentially drug-related SAEs			
AE leading to discontinuation			
Yes			
No			
AE leading to death			
Yes			
No			
Ongoing			
Yes			
No			
Outcome			
Unchanged			
Worsened			
Recovered/resolved with no sequelae			
Recovered/resolved with sequelae			
Death			

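### SAP Table 18 counts systemic allergic symptoms as events; the proportion of children with them, which the protocol requires by treatment, appears in no SAP table

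*SAP*

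**What the plan says.** **Systemic allergic symptoms.** SAP section 2.2.6 lists these symptoms, and the potentially drug-related ones, as safety endpoints e and f, without saying whether the unit is the child or the event. Protocol section 12.11 makes any systemic allergic reaction related to the patch an adverse event of special interest. Protocol section 13.6.6.1 states the unit: "The proportion of subjects that experience systemic allergic symptoms will be summarized by treatment". The same section also lists potentially drug-related systemic allergic symptoms among the events whose incidence is to be summarized.

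In the SAP, the text of section 4.5.1 does not name these symptoms. Its description of Table 18 ends with "any serious AEs, AEs leading to discontinuation and death, ongoing AEs, and outcome) by treatment group will be presented". The Table 18 shell in section 5.1 has the row "Number of systemic allergic symptoms" with a yes/no split by potential drug-relatedness.

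**Action codes.** The coding note to listing Tables 16A and 16B reads "Action taken: 0=None, 1=Prescribed medication, 2=Non-medication treatment, 3=Hospitalization or prolongation, 4=Discontinued treatment". SAP safety endpoint c is "Discontinuation due to TEAEs". Protocol section 8.4.3.1 says "The patch treatment will be temporary discontinued for any subject with Grade 4 local skin reactions" when these are related to the product. Protocol section 8.5.6 adds, for severe local reactions, that "the daily duration of patch application should be adapted/reduced if necessary, to limit the severe reactions" and, for systemic symptoms including worsening EoE, a "possible decrease in daily exposure to the Viaskin patch with gradually increase in exposure as tolerated".

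**The concern.** The arms are unequal by design, and the patch is applied daily. Under protocol section 8.5.6, a patch removed for a systemic reaction is re-applied the next day, so repeat events in one child are foreseeable. In that setting a total number of symptoms depends on arm size and on how often the most reactive child reacts. The number of children affected is what a reader of a small pilot needs, and it is the figure the protocol promised. If the report follows the SAP shells, the summary of an event of special interest will be one that cannot be compared between arms.

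The action code raises a lesser question. The protocol uses the same verb for a temporary stop of the patch and for leaving the study. The SAP code for discontinued treatment does not say which it means, and no code exists for interruption or reduced wear.

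**Working it through.** The plan states no figure on this point to reproduce. The check is a comparison of texts, with a short illustration on assumed counts.

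**1. What unit does the Table 18 row use?** Table 18 opens with a row for the number and percentage of subjects with AEs, followed by a separate row for the number of AEs. The table therefore writes out the subject unit when it means subjects. The systemic allergic row does not, so it reads as an event count.

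**2. Can the proportion be found in another SAP table?**
- Table 17A counts subjects, but by system organ class only. Systemic allergic symptoms have no row of their own there.
- Table 17B counts events.
- Table 19A is the subject-level table of treatment-emergent events. It has no systemic allergic row.
- Table 19B counts events and has no such row either.
- Table 20 covers local skin reactions only.

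None of these supplies it.

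**3. What does an event count leave open?** Denominators are 16 active and 6 placebo (SAP section 2.4.2; protocol section 13.2). Assume six symptoms in the active arm. The 95% intervals are Clopper-Pearson: lower limit = the 0.025 quantile of Beta(x, n − x + 1), upper limit = the 0.975 quantile of Beta(x + 1, n − x).

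| Source of the six symptoms | Table 18 entry | Children affected | 95% CI |
|---|---|---|---|
| One child, six episodes | 6 | 1/16 = 6.3% | 0.2% to 30.2% |
| Six children, one each | 6 | 6/16 = 37.5% | 15.2% to 64.6% |

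SAP section 3.2 gives 15 and 5 children instead. With those numbers the two rows become 1/15 = 6.7% and 6/15 = 40.0%, and the conclusion is the same.

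**4. Are the counts comparable between arms?** With the same mean number of symptoms per child, r, in both arms, the expected counts are 16r and 6r. Their ratio is 16/6 = 2.67 (15/5 = 3.0 with the section 3.2 numbers), although there is no difference per child.

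**5. The action code.** Of the five codes, only code 4 refers to the patch. The protocol names two actions short of leaving the study: temporary discontinuation (8.4.3.1) and shorter daily wear (8.5.6). Neither has its own code, and the SAP does not define code 4 as temporary or permanent. As an assumed example, suppose three of 16 active children had a temporary stop and none stopped for good. If the rows for events leading to discontinuation were filled from this code, they could show 3/16 = 18.8% or 0/16, depending on how code 4 was read. No passage says that those rows are filled that way, so this shows the ambiguity and does not predict a result.

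**The case against.** **The listings already show it.** With about 22 children, SAP section 4.5.1 lists every AE by treatment group and subject, and section 4 says that listings will sometimes be the most informative presentation. A reader could therefore tell one child with six episodes from six children with one each. This softens the point, but a listing is not the summary by treatment that the protocol requires. The fields named in 4.5.1 also include no marker for a systemic allergic symptom.

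**The protocol commitment still stands.** The SAP is meant to expand on the protocol, and a missing shell row does not revoke section 13.6.6.1. That is correct. But tables are programmed from shells, and the shell that exists specifies a different quantity.

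**No formal safety comparison is planned.** Both documents say so, and no test is affected. The protocol nevertheless asks for the figure by treatment, and readers will set the two columns side by side.

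**A stronger reading.** A reader might infer that the SAP misreports two of its own safety endpoints. The documents do not support that:
- Endpoints e and f state no unit, so an event count departs from the protocol and not from the SAP's own endpoint.
- Interruption and reduced wear are not among SAP endpoints a to g.
- Discontinuation due to TEAEs has a subject-level row in Table 19A.
- SAP section 4.3 and Table 5 separately report discontinuation of each period, with the primary reason listed.
- The AE form is not in the documents and may hold more detail than the code list.

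**Conclusion.** The point holds for systemic allergic symptoms. The protocol requires a proportion of children by treatment, and the SAP shells provide only a number of symptoms. For the same printed count of six, the proportion of active children affected could be anywhere from 6.3% to 37.5%, and the 16-to-6 split alone gives a count ratio of 2.7 under equal rates per child. The counts are assumed; the mismatch of units is not. It rests on reading the Table 18 row as events, which the wording of its neighbouring rows supports.

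The action code is a clarification only. It is undefined as to temporary or permanent stops, but nothing shows that the discontinuation rows would be wrong. Both matters concern safety reporting and leave the primary efficacy analysis untouched. They are worth correcting because safety is a stated study objective and the correction is cheap.

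**What to change.** **Main change.** In Table 18 or Table 19A, report by arm n (%) of children with at least one systemic allergic symptom, and n (%) with at least one potentially drug-related one. Keep the event count as a second line. Name the output in section 4.5.1.

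**Secondary clarification.** In the Tables 16A/16B coding note, define code 4 as permanent discontinuation and add a separate code for interruption or reduced wear. The rows for events leading to discontinuation should then agree with the Table 5 disposition data. This concerns how events are recorded and reported; no rule for managing reactions is proposed.

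**Cost.** One or two shell rows, a sentence of SAP text and a code-list edit. The new rows need only the symptom records that already feed Table 18, counted once per child. Recoding past interruptions may be incomplete. Protocol section 11.11 asks for the reason for early removal only in the first 3 months of diary use. After that, subjects report only the days or periods when the patch was not applied per protocol, so reasons for shortened wear may not be recoverable from the diary.

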#### 4.1 Analysis populations

The analysis populations are:

- **Safety population:** The safety population is comprised of all subjects who are randomized and received at least one dose of study treatment and all subjects in the control group who did not withdraw or were not withdrawn. This population will be used to assess comparative safety information.
- **Intent-to-treat population:** The intent-to-treat (ITT) population (full analysis set) is comprised of all subjects who are randomized. Subjects in the ITT population will be categorized by their randomized treatment assignment. This population will be used to assess comparative efficacy information.
- **Per protocol population:** The per protocol (PP) population includes all subjects in the ITT population who do not have pre-defined major deviations from the protocol that may affect the primary (and secondary) endpoints (i.e., subjects who have not gone through the third upper endoscopy and biopsy at the end of the double-blind treatment, subjects with a compliance below 80%, etc.). The PP population will be used to perform confirmatory analyses of the primary efficacy evaluation.

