## 4.3 Subject disposition

Subject disposition will be summarized for the ITT population. Subjects in each study population (ITT, PP, and Safety), subjects who received study medication, and subjects who completed and discontinued the double-blind period as well as the open-label period will be summarized (e.g., frequency counts and percentages) by treatment groups and overall (*Table 5*). The primary reason for discontinuation from the double-blind period and the open-label period will be listed by treatment groups.

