# Hodges-Lehmann estimate with 95% CI for median differences between two treatment groups will be reported.

### Table 12 specifications

Repeat with ITT population and PP population separately as Table 12A and Table 12B, respectively.

Table 13A. Summary Statistics for Response rate at the End of the Double-blind Treatment (Secondary Efficacy Endpoint)

	All	Viaskin® milk	Placebo	Relative Risk (95% CI)
Response rate, n (%)				
Excellent ( $\leq 1$ eosinophils/HPF)				
Good (2-14 eosinophils/HPF)				
Poor ( $\geq 15$ eosinophils/HPF)				
Values will be expressed as frequency counts (percentages).				

Table 13B. Summary Statistics for Response rate at the End of the Open-label Treatment (Secondary Efficacy Endpoint)

	All	Viaskin® milk	Placebo	Relative Risk (95% CI)
Response rate, n (%)				
Excellent ( $\leq 1$ eosinophils/HPF)				
Good (2-14 eosinophils/HPF)				
Poor ( $\geq 15$ eosinophils/HPF)				
Values will be expressed as frequency counts (percentages).				

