Table 19A. Treatment-Emergent AEs (TEAEs)\* by Treatment Groups  
(Number of subjects (%))

	All	Viaskin® milk	Placebo
TEAEs			
Potentially drug-related TEAE			
Severity of TEAE			
Mild			
Moderate			
Severe			
Life-threatening			
Death			
Serious TEAE			
TEAE leading to discontinuation			
TEAE leading to death			
Number of TEAEs			
0			
1			
2			
3 +			
Ongoing			
Yes			
No			
Outcome			
Unchanged			
Worsened			
Recovered/resolved with no sequelae			
Recovered/resolved with sequelae			
Death			

\* Treatment-emergent AE is defined as any AE, regardless of relationship to study drug, which occur during AE collection period of study drug or an event already present that worsens in either intensity or relationship to study drug following exposure to Viaskin®.

Table 19B. Treatment-Emergent AEs (TEAEs)\* by Treatment Groups  
(Number of TEAE)

	All	Viaskin® milk	Placebo
Number of TEAEs			
Number of potentially drug-related TEAE			
Number of severity of TEAE			
Mild			
Moderate			
Severe			
Life-threatening			
Death			
Number of serious TEAE			
Number of TEAE leading to discontinuation			
Number of TEAE leading to death			
Number of TEAEs per subject			
0			
1			
2			
3 +			
Number of local TEAE			
Number of severity of local TEAE			
Mild			
Moderate			
Severe			
Life-threatening			
Death			
Outcome			
Unchanged			
Worsened			
Recovered/resolved with no sequelae			
Recovered/resolved with sequelae			
Death			

\* Treatment-emergent AE is defined as any AE, regardless of relationship to study drug, which occur during AE collection period of study drug or any event already present that worsens in either intensity or relationship to study drug following exposure to Viaskin®.

Table 20. Summary Statistics of Local Skin Reactions (Adverse Events)

	All	Viaskin® milk	Placebo	
Number of patients with reactions				
0				
1				
2				
3				
4				

Values will be expressed as frequency counts (percentages) unless indicated.

Table 21. Summary of Laboratory Abnormalities based on CTC Grade by Visit and Treatment Groups

	Viaskin®Milk				Placebo				
	Visit 1	Visit 8	Visit 10	Visit 16	Visit 1	Visit 8	Visit 10	Visit 16	
Hematology									
RBC Count									
WBC Count									
Hemoglobin									
Hematocrit									
Platelet Count									
Segmented Neutrophils									
Lymphocytes									
Monocytes									
Eosinophils									
Basophils									
Chemistry									
Total Protein									
Blood Urea Nitrogen									
Creatinine									
ALP									

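### The SAP's adverse-event summary tables have one Placebo column and no study period, although every child continuing after Visit 10 wears the active patch

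*SAP*

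**What the plan says.** **Summaries.** SAP 4.5.1 summarises adverse events and treatment-emergent events by treatment group. The overview of treatment-emergent events ends with "any serious TEAE, any TEAE leading to discontinuation and death) by treatment groups will be provided". Table 18 is titled "Summary of Adverse Events by Treatment Group" and Table 20 "Summary Statistics of Local Skin Reactions (Adverse Events". These two shells and 19A and 19B have the columns All, Viaskin milk and Placebo. No title, column or footnote in them names a period.

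**Collection and treatment.** Protocol 12.1 records adverse events from screening consent to the End of Study visit. Under protocol 8.5.1 and SAP 2.3, all children receive open-label Viaskin Milk after the third endoscopy at Visit 10, for up to 11 further months.

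**Assignment.** SAP 4.1 says "Subjects in the ITT population will be categorized by their randomized treatment assignment". It gives no matching sentence for the safety population, which is the one used for comparative safety.

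**Repeated events.** When a treatment-emergent event recurs with different severity or relatedness, protocol 13.6.6.1 says "then the TEAE will be assigned to the highest severity category and/or most related relationship category". It sets no period for this.

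**Elsewhere the SAP separates the periods.** Under SAP 4.3, "subjects who completed and discontinued the double-blind period as well as the open-label period will be summarized". Table 13B is "Summary Statistics for Response rate at the End of the Open-label Treatment (Secondary Efficacy Endpoint", alongside 13A for the double-blind period. Table 21 is "Summary of Laboratory Abnormalities based on CTC Grade by Visit and Treatment Groups", and Table 22 is also by visit.

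**The concern.** Safety is one of the trial's two stated objectives, and a placebo-controlled comparison of adverse events exists only up to the switch at Visit 10. A table that runs through the open-label year under a Placebo heading no longer shows that comparison. It also hides what happens when children move from placebo to the active patch, a group that protocol 8.5.1 singles out when it repeats the gradual increase in wear time. Because no formal test of adverse events is planned, the descriptive tables are the safety result, so their periods and denominators need to be defined.

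**Working it through.** The plan states no figure on this point, so there is none to reproduce. The check has three steps.

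**1. Does any text separate the periods for these tables?** I looked in SAP 4.1, 4.5, 4.5.1 and shells 18 to 22, and in protocol 12.1, 13.6.6.1 and Appendix 3. The only time wording attached to treatment-emergent events is the collection period for study drug, which the SAP does not define. The recording window in protocol 12.1 spans both treatment periods. Nothing divides the events at Visit 10. The column layouts of Tables 16A to 17B are not visible in the text available to me, so I draw no conclusion about them.

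**2. What does Placebo mean in these columns?** Tables 3, 4A, 4B, 8, 9B, 10 to 12, 13B, 14 and 15 all keep a Placebo column at Visit 16 or the end of open-label treatment. Table 21 keeps one at Visit 16, and Table 22 at Visits 11 to 17. No child is on placebo then, so in those tables Placebo can only mean the randomised arm. The natural filling of Tables 18 to 20 follows the same convention. The difference is that the other tables also show visit or period.

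**3. How much active-patch time would the Placebo column hold?**
- Inputs: up to 11 months double-blind and up to 11 months open-label (SAP 2.4.3); 6 placebo children (protocol 13.2, SAP 2.4.2) or 5 (SAP 3.2).
- Share for a completer = open-label time / (double-blind + open-label time) = 11 / (11 + 11) = 50%.
- Patch-months with 6 children: 6 × 11 = 66 active, out of 6 × 22 = 132. With 5 children: 5 × 11 = 55, out of 5 × 22 = 110. These are maxima, because they assume that nobody drops out.
- Unequal periods: each period is nominally 9 months plus 1 week to 2 months of milk, so about 9.25 to 11 months. The extremes are 9.25 / (11 + 9.25) = 46% and 11 / (9.25 + 11) = 54%. These are not strict bounds, because visit windows and the permitted delay of up to 7 days to the first open-label patch can move them slightly. The protocol asks for matching milk periods, which keeps the share near 50%.
- One child's weight in a row that counts subjects: 1/6 = 16.7 points, or 1/5 = 20 points. A placebo-arm child moves the row by that much only if the first event of that kind falls in the open-label period. A child already counted from the double-blind period does not move it.

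**Severity rule.** Suppose a placebo-arm child has a mild reaction before Visit 10 and a severe one of the same kind after it. Under protocol 13.6.6.1 with no period, that child is counted once, as severe, in the Placebo column.

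**The case against.** The strongest reply is that little is lost. SAP 4.5 plans no formal analysis of safety endpoints. The listings described in SAP 4.5.1 carry treatment group, subject, start date and stop date. SAP section 4 says that with so few children, listings may be the most informative display. With 5 or 6 placebo children, a reader could rebuild the split by hand, apart from events on the day of the switch. This stands, and it limits the weight of the point. It does not supply a summary rule, and the tables would still show a mixed Placebo column.

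Two stronger readings are tempting, and the documents do not support them.
- **That nobody can tell what Placebo means.** SAP 4.1 does lack an assignment rule for the safety population, but the SAP's other tables make the randomised-arm reading clear enough. The defect is the missing period.
- **That the difference between the arms would shrink by a known amount.** The documents give no adverse-event rates on either patch and nothing on how events in the two periods relate within a child. Any such figure would rest wholly on assumed rates. The 50% is a share of exposure, not of events.

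**Conclusion.** The point holds and should be fixed before database lock, as a matter of moderate weight. Filled by the SAP's own convention, Tables 18, 19A, 19B and 20 would present as Placebo a column in which about half of a completer's patch time is on the active patch (up to 66 of 132 patch-months with 6 children, 55 of 110 with 5). The highest-severity rule could also carry an open-label severity into that column. This rests on the randomised-arm reading, on completers, and on periods of similar length. The direction and size of the effect on the between-arm comparison cannot be given from the documents. A reader might infer that the safety data are compromised. They are not: the events remain dated in the listings, and only the summary is defective.

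Two nearby matters are separate and minor, and add no weight here: when the treatment-emergent window starts (SAP 4.5.1 and protocol 13.6.6.1 against Appendix 3), and the control-group clause that SAP 4.1 adds to the safety population.

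**What to change.** Make the change in the SAP only. Protocol 13.3 lets the SAP expand on the protocol's methods, whereas protocol 17.2 would require a formal amendment for a protocol edit.

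1. Split Tables 18, 19A, 19B and 20 into a double-blind part (Viaskin, Placebo) and an open-label part (Viaskin-to-Viaskin, Placebo-to-Viaskin), each with its own denominators. Do the same for 17A and 17B if their layouts lack a period.
2. Assign each event by onset date relative to a stated cut point: the first open-label patch, or Visit 10 where that patch date is not recorded. The fallback matters because the first open-label patch may be postponed by up to 7 days. Diaries record daily application times only for the first 3 months, and the protocol does not say that this restarts at the switch.
3. Pre-specify a rule for onset on the switch day. Protocol 12.1 records time of occurrence, which can help. Visit 10 is also the research endoscopy after milk reintroduction, so sending all untimed same-day events to the open-label part would take procedure-related or milk-related events out of the blinded comparison. The choice should be deliberate.
4. Apply the highest-severity and closest-relationship rule within each period, and state how an event that begins before the cut point and worsens after it is counted. The documents do not say whether a date of worsening is recorded.

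**Cost:** SAP wording, revised shells and more tables, with small counts per cell. Start dates are already collected, and no visit or procedure changes.
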